## 1 List of Abbreviations

CBO	Community-based organization
CDC	Centers for Disease Control and Prevention
CI	Confidence interval
GD	Guangdong Province
GEE	Generalized estimating equations
GLMM	Generalized linear mixed models
HIVST	HIV self-testing
MSM	Men who have sex with men
RCT	Randomized controlled trial
SD	Shandong Province
SESH	Social Entrepreneurship for Sexual Health Group
SMS	Short Message Service text message

## 2 Summary

Crowdsourcing may be a useful tool for spurring innovation in HIV test promotion campaigns. Crowdsourcing is the process of shifting a task from an individual to a group, often in the form of an open contest. The purpose of this stepped wedge randomized controlled trial is to evaluate the effectiveness of a crowdsourced intervention on promoting HIV testing among Chinese MSM. The crowdsourced intervention will include an open contest, judging to determine finalists and prizes, a designathon, and contest-based MSM engagement. The hypothesis is that a crowdsourced intervention will be superior to conventional HIV test uptake campaigns in eliciting HIV test uptake.

# **3** Introduction

## 3.1 Background

Key population HIV testing, especially among young key populations, is urgently needed. However, many young key populations are not well reached by conventional HIV testing campaigns. Operational research has demonstrated that many HIV testing campaigns do not reach them. This is the case in China where approximately 40% of men who have sex with men (MSM) have never received HIV testing. Low levels of MSM community engagement, hesitancy to access facility-based services, and low trust in facility-based services all constrain MSM HIV testing programs in China.

Preliminary data from our team suggests that crowdsourcing may be a useful tool to overcome these challenges and increase HIV test uptake among MSM. An online RCT found that 37% of MSM without any HIV test experience who viewed a crowdsourced video subsequently reported receiving first-time HIV testing within one month. Qualitative data from our research group has shown that crowdsourcing contests empower individuals and result in a range of community engagement.

## 3.2 Specific Aims and Hypotheses

Specific Aim 1: To compare HIV test uptake associated with a crowdsourced intervention to that associated with conventional HIV test uptake campaigns. Hypothesis 1: A crowdsourced intervention is superior in eliciting HIV test uptake compared to conventional HIV test uptake campaigns.

Specific Aim 2: To compare secondary outcomes (including incremental cost, condom use, HIV testing social norms, syphilis testing, etc.) of a crowdsourced intervention to those of conventional HIV test uptake campaigns.

Hypothesis 2: A crowdsourced intervention is superior in promoting a range of healthy behaviors and HIV testing social norms.

## 4 Trial Design

## 4.1 Type of Trial

This study will use an adaptation of the stepped wedge randomized controlled trial (RCT) design (Figure 1). In the stepped wedge RCT, study sites are randomized to begin the intervention at different times so that by the end of the study period all sites have initiated the intervention. A total of eight major metropolitan cities - four from Guangzhou Province (Guangzhou, Jiangmen, Zhuhai, Shenzhen) and four from Shandong Province (Yantai, Jinan, Qingdao, Jining) - will implement the crowdsourced intervention. These cities were chosen based on the following criteria: 1) previous CDC MSM sentinel surveillance site; 2) capacity

for campaign implementation; 3) capacity for intervention implementation at community level. Four cities (Guangzhou, Shenzhen in Guangdong Province, Qingdao, and Jinan in Shandong Province) will implement more intensive in-person events to promote engagement during the intervention development phase. Intervention development and implementation are described in detail in later sections.

## 4.2 Rationale for Trial Design

A number of factors influenced our decision to adopt a pragmatic stepped wedge RCT design. Unlike a tightly controlled explanatory trial, a pragmatic trial evaluates an intervention in a real life context. We aim to understand whether crowdsourced interventions work in the range of local settings. A pragmatic design allows us to examine this intervention in eight different cities. In addition, two previous studies demonstrate that crowdsourcing can enhance HIV interventions among MSM. Given that we will recruit MSM with a known high risk of acquiring HIV infection, withholding our intervention to a subgroup of participants would be difficult. A stepped wedge RCT design addresses this ethical concern by ensuring all participants receive the intervention.

## 4.3 Randomization and Stratification

The eight cities will be randomized to initiate intervention in groups of two at three-month intervals (Figure 1). The order of intervention implementation at four cities within each province (Guangdong and Shandong Provinces) will be randomized using SAS software. One city in Guangdong Province and one city in Shandong Province will then begin intervention simultaneously, i.e. city-level randomization will be stratified by province. While waiting to initiate the intervention, cities will continue conventional campaigns that are part of the routine activities of local CDC and CBOs.

Phase	Pre	p.		Inte	erver	ntior	ı									
Months	1	2	3	4	5	6	7	8	9	10	11	12	13	14	15	16
CDC surveillance survey																
Develop intervention and recruit online cohort in 8 cities																
Guangzhou (GD)				*			*			*			*			*
Yantai (SD)				*			*			*			*			*
Jiangmen (GD)				*			*			*			*			*
Jinan (SD)				*			*			*			*			*
Zhuhai (GD)				*			*			*			*			*
Qingdao (SD)				*			*			*			*			*
Shenzhen (GD)				*			*			*			*			*
Jining (SD)				*			*			*			*			*

Figure 1. Stepped-wedge study design

\*represents online survey at baseline and every 3 months thereafter. Gray shading represents roll-out of the intervention. 8 city clusters; 5 time periods; randomization stratified by 2 provinces (Guangdong, Shandong)

## 5 Trial Population and Measures

## 5.1 Eligibility

Eligibility criteria will include: currently living and planning to live in the eight cities for the next 12 months; not living with HIV; no HIV test in the past three months; born biologically male and identify as either male or transgender; had oral or anal sex with men at least once during their lifetime; 16 years and older; willing to provide cell phone number (for follow up and incentive delivery purposes); completed the informed consent document. MSM who meet all other eligibility criteria but received testing in the past three months or living with HIV will be invited to complete a single survey, but not followed over time in the cohort.

### 5.2 Recruitment

## 5.2.1 Online Recruitment

We will build our questionnaire on Sojump Survey Software (Sojump, Shanghai, China). Men will enter the study through website and social media banner/word advertisements, yet only those who lived in the 8 study cities could launch the questionnaire with the survey platform's IP address restriction function. China's largest gay app, BlueD, will be used to target recruitment within the eight cities. Eligible men will be invited to join the online cohort. No names or addresses will be collected from participants. In addition to the direct recruitment through websites and social media advertisements, participating individuals will be invited to refer up to three friends from their social networks, and 10 RMB will be given to them as incentive for each eligible participants they successfully invited. All individuals who enroll in the study will receive a 50 RMB (8.50 USD) pre-paid cell phone card for the first follow up and 50 RMB for each subsequent follow up. Those who complete all surveys will be given an opportunity to win an iPad mini. Surveys will be given at baseline and every three months thereafter (Figure 1).

## 5.2.2 CDC Data Collection

MSM surveillance sites in each of the eight cities will have additional questions added about viewing SESH images, social media engagement with SESH, contributing to SESH contests,

exposure to other ongoing campaigns, HIV/syphilis testing, HIV/syphilis test results. All men who enter surveillance sites in these cities will also be invited to take part in the online cohort. Following informed consent, cell phone numbers will be used to link CDC and online survey data sets.

#### 5.3 Measures

Information on socio-demographics, sexual behaviors, and psychosocial conditions will be collected using standardized online survey tools. Socio-demographic characteristics include participants' age, highest level of education completed, annual income, marital status, sexual orientation, and sexual orientation disclosure. Behavioral and psychosocial variables include self-reported HIV testing, syphilis testing, HIV self-testing, HIV test-associated stigma, frequency of sex, condom use (condomless sex, sex always with condom, and no sex), HIV testing social norms, HIV testing self-efficacy, community engagement, campaign engagement, MSM empowerment.

## 6 Intervention

#### 6.1 Intervention Development

The intervention will be developed from a nationwide crowdsourcing contest and a designathon (Figure 2). The crowdsourcing contest will generate intervention materials that will later be packaged via the designathon into core elements of an HIV testing campaign. This ensures crowd wisdom is utilized through the entire intervention, from idea generation to campaign implementation.

## 6.1.1 Crowdsourcing contest

The first part of the crowdsourcing contest will be an open call for concepts (< 500 characters) or images (photographs, posters, drawings, etc.) promoting HIV testing among young men in China. This open call will be announced on social media platforms nationwide. Social media promotion will include QQ, Weibo, WeChat announcements and short videos explaining the contest from SESH and our community partners in each city (CBOs and student groups interested in HIV testing). Social media will also serve as a channel for announcing prizes, deadlines, and other relevant information. Four cities (Guangzhou, Shenzhen in Guangdong Province, Qingdao, and Jinan in Shandong Province) will

implement in-person events in addition to social media promotion. In-person events will include community-based introductions, interactive feedback sessions, and community-driven events (decided by community partners). Multiple incentives, including chances to win an iPad Mini, cash, post cards, etc., will be included to encourage contest participation.

Crowdsourced entries will be evaluated by a crowd panel and an expert panel. The crowd panel consists of MSM from each of the eight cities while the expert panel consists of professionals from CDC, CBOs, and universities in the eight cities. These local panels increase the likelihood that local preferences would be incorporated, which may facilitate later implementation. The quality of crowdsourced ideas will be judged based on four established dimensions: novelty, relevance, feasibility, and elaboration. Judges will consider the four dimensions and score an entry on a 10-point scale. Given that a large number of judges evaluating a relatively small number of entries have been shown to be internally consistent and externally valid, each judge in our contest will evaluate no more than 20 entries. Based on the number of entries, we will ensure enough judges are recruited so that each entry has at least three independent ratings. Following these judging criteria, all entries will first be screened to check for relevance to our contest and plagiarism. Next, 40 concepts and/or images will be identified by the crowd panel and expert panel. Scores from the expert panel will be used to announce contest winners. All 40 concepts and/or images will be recognized as finalist entries and be presented as materials for the designathon. The crowdsourcing contest and judging are planned to span a three-month period.

### 6.1.2 Designathon

The designathon will use finalist concepts and/or images to develop core elements of an HIV testing campaign. A designathon is similar to a hackathon, but focused instead on designing a campaign. Teams are formed with an emphasis on multi-sectoral partnership. Each team consists of one CDC worker and one MSM CBO leader from each of the eight cities as well as three participants selected from a nationwide application. A group of mentors from communication, design, social work, and public health background will also be available for consultation to all teams. Teams will have 72 hours to brainstorm and generate a written intervention plan that incorporates concepts and images from the crowdsourcing contest. A group of judges will evaluate team entries and select design elements to be included in a final, HIV test promotion campaign. Winners will be recognized with awards.

The final campaign will be implemented at both the individual and community levels using social media, in-person events, and other crowdsourced ideas for implementation. After the RCT is complete, we will launch an image bank that allows free access to images/taglines/concepts developed as part of the contest.

#### 6.2 Intervention Implementation

Phased implementation will be carried out in the eight cities following the stepped wedge RCT design (Figure 1). Implementation in each city will be locally adapted based on crowd feedback from the contest and the designathon. The intervention will be implemented at the individual level (via WeChat messages and SMS) and at the community level (via community partners including CDC, CBOs, and social media influencers) (Figure 2).

For individual-level implementation, the campaign content (images and/or concepts) will first be shown to the online cohort at the end of the baseline survey, and then repeated once every two weeks for the next three months. Half of the online cohort will receive the campaign content via WeChat message while the other half will receive the campaign content via SMS text message. For community-level implementation, community partners in each city will facilitate the campaign using crowdsourced implementation ideas generated from the designathon.

Figure 2. Schematic diagram of intervention development and implementation.

\*Finalist entries will be selected after an initial screening followed by crowd panel and expert panel judging (Detailed under "Crowdsourcing contest").

\*\*Crowdsourcing contest winners will be selected based on expert panel scores.

\*\*\*Individual-level implementation will be divided based on delivery method into two groups: intervention via WeChat message vs. intervention via SMS text message.

a: Crowd involvement in crowdsourcing contest consists of a nationwide, open call for submission of concepts and/or images related to promoting HIV testing among untested individuals.

b: Crowd involvement in designathon consists of multi-sectoral team members working with guidance from professionals to design an intervention plan.
c: Crowd involvement in community-level implementation entails participation in contests and campaign events held by local CDC and CBOs.

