## 7 Statistical Considerations

#### 7.1 Primary Outcomes

The primary outcome of this study will be HIV test uptake over the previous three months. This will be assessed by self-report during follow up survey and triangulated with HIV testing surveillance data from the CDC. A difference of 10% in testing rate (assuming a proportion of HIV testing of 35% during the crowdsourced intervention period and 25% during the conventional intervention period) was chosen based on existing levels of HIV testing and what would be feasible and have public health importance in the Chinese context. The CDC measurement of the primary outcome will be the difference between HIV testing comparing the three months immediately prior to the intervention and the three months of the intervention.

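### Section 6.2 first shows campaign content to the whole online cohort at the baseline survey, which conflicts with the phased start by city in Sections 4.3 and 6.2 and with the survey calendar in Figure 1

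*Combined protocol and SAP*

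**What the plan says.** Section 6.2 opens with the phased roll-out: "Phased implementation will be carried out in the eight cities following the stepped wedge RCT design (Figure 1"). It then names two levels of implementation, individual (WeChat and SMS) and community. On the individual level it states that "the campaign content (images and/or concepts) will first be shown to the online cohort at the end of the baseline survey", followed by fortnightly repeats over three months. It divides the whole online cohort into a WeChat half and an SMS half. Neither sentence is limited to cities that have started.

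Section 4.3 sets the randomised calendar: "The eight cities will be randomized to initiate intervention in groups of two at three-month intervals (Figure 1"). It also defines the control condition: "While waiting to initiate the intervention, cities will continue conventional campaigns that are part of the routine activities of local CDC and CBOs".

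Figure 1 marks surveys at months 4, 7, 10, 13 and 16 in every city row. Its legend explains that the asterisk "represents online survey at baseline and every 3 months thereafter", and Section 5.2.1 uses the word in the same way: "Surveys will be given at baseline and every three months thereafter (Figure 1").

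**The concern.** The primary model in Section 7.4.1 has fixed terms for calendar time and for intervention status, and random terms for site and person. It estimates the effect by comparing, within each period, cities that have started with cities still waiting. That comparison needs the waiting cities to be unexposed. If one of the two named levels of implementation reaches all eight cities on the same date, the time terms absorb what the cities share, and the intervention term measures less than the full package. Staff could send messages in all eight cities at month 4 and still comply with the Section 6.2 sentence. Exposure cannot be withdrawn afterwards, and a null result would then be hard to interpret.

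**Working it through.** **The passages side by side**

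| Source | Month 4, first pair of cities | Month 4, other six cities |
|---|---|---|
| Section 6.2, individual-level sentence with the Figure 1 survey dates | content shown | content shown |
| Section 4.3 and the opening of Section 6.2 | intervention starts | conventional campaigns only |

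The two rows agree for two of the eight cities.

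**Plan's own figures.** Section 7.3 and Table 2 (35% against 25%, coefficient of variation 0.4) give 91 men per city before loss. 91/(1 − 0.30) = 130, and 130 × 8 = 1040, as stated. The 91 itself does not follow from the cited formula with five periods and two cities per step, which gives 64 to 73 across the variance choices tried. That is a separate matter and does not bear on this point. It is used below only as a sample size, alongside 160 × 0.70 = 112, the planned enrolment after loss.

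**Affected city-periods.** Starts are read as months 4, 7, 10 and 13. The baseline survey is not counted as a control period, because eligibility requires "no HIV test in the past three months" and the outcome there is zero by design. Waiting cities at the month 7, 10, 13 and 16 surveys number 6, 4, 2 and 0, so 12 of the 8 × 4 = 32 follow-up city-periods are control. Literal messaging falls in the first interval: 6 of the 12.

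**Model for the size.** This is the stepped-wedge linear model cited in Section 7.3, with I = 8 cities, T = 4 follow-up periods, σ² = 0.30 × 0.70/n and τ = 0.4 × 0.25 = 0.10. From the layout, U = 20, W = 2² + 4² + 6² + 8² = 120 and V = 2(16 + 9 + 4 + 1) = 60.

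Var = Iσ²(σ² + Tτ²) / [(IU − W)σ² + (U² + ITU − TW − IV)τ²] = 8σ²(σ² + 4τ²) / (40σ² + 80τ²)

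- n = 91: σ² = 0.002308, SE = 2.96 points.
- n = 112: σ² = 0.001875, SE = 2.68 points.

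Power = Φ(estimate/SE − 1.96). For the planned 10 points this is 92% and 96%.

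**Expected estimate.** Let m be the share of the 10-point effect carried by messages; the documents give no value.

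- *Messages repeated at each city's start, no carry-over of early exposure.* The least-squares weights per city on the waiting pairs at month 7 (n = 91) are −0.1397, −0.0500 and +0.0397. With two cities per pair they sum to 2 × (−0.1500) = −0.30, so the estimate is 10(1 − 0.30m). The sum is also −0.30 at n = 112.
- *Not repeated at a city's start.* The message effect is then common to all cities in each period. The weights sum to zero within every period, so it drops out and the estimate is 10(1 − m), whatever the persistence.
- *Repeated, but the early effect persists in full.* Waiting cities already carry 10m points in every period, so the estimate is again 10(1 − m).

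| m | Repeated, no carry-over | Power, n = 91 / 112 | Not repeated, or full persistence | Power, n = 91 / 112 |
|---|---|---|---|---|
| 25% | 9.25 | 88% / 93% | 7.5 | 72% / 80% |
| 50% | 8.5 | 82% / 89% | 5.0 | 39% / 46% |
| 75% | 7.75 | 75% / 82% | 2.5 | 13% / 15% |

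Intermediate cases lie between: with repeats, half carry-over and m = 50%, the estimate is 6.75 points and power 63% at n = 91.

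**Limits.** These figures omit the individual random effect. With an assumed within-man correlation of 0.2, the SE at n = 91 falls to 2.66 points and the expected estimates do not change. The planned logit-scale mixed model was not simulated.

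**The case against.** The best defence is that the opening sentence of Section 6.2 governs what follows. The same paragraph makes individual messaging part of the phased intervention, so the later sentence may only describe the order of content within each city's roll-out, with the word baseline used loosely. Two details support this. The three-month message period equals the step length, and Section 7.1, describing the CDC measure, contrasts "the three months immediately prior to the intervention and the three months of the intervention". The Figure 1 shading and the Figure 2 drawing, which might settle the matter, are not available here.

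This reading is plausible and may be what was intended. It does not remove the inconsistency: no available text defines baseline city by city, and the survey marks in Figure 1 give one shared date.

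A reader might infer three stronger things, none of which the documents support. The first is that waiting cities were in fact messaged early; the text shows only that this would comply with one sentence. The second is that the stepped-wedge layout is itself at fault; the fault lies in the wording of one sentence. The third is that the estimate would necessarily lose the whole message component; that follows only if messages are not repeated at a city's start or the early effect persists in full. Otherwise the estimate is diluted but still includes messages.

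**Conclusion.** The point stands as an internal inconsistency: as written, the individual-level sentence in Section 6.2 cannot be followed together with Section 4.3 in six of the eight cities. Confidence is medium, because the authors may have meant each city's own start. If the sentence were followed literally and messages raise testing, the bias is toward no effect. Its size is a range: for message shares of 25% to 75%, the expected estimate runs from 9.25 down to 2.5 points against a planned 10, and power at 91 men per city from 88% down to 13% against 92%. The range rests on the assumed share, repetition and persistence, on starts at months 4, 7, 10 and 13, and on a linear model. Because the wording decides when randomised exposure begins, and is cheap to settle, it should be corrected despite the plausible benign reading.

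**What to change.** Reconcile the individual-level sentence in Section 6.2 with that section's opening, Section 4.3 and Figure 1, and state which survey baseline means there. Individual-level exposure and the intervention-status variable in the primary model should follow the same calendar in each city. Record the date on which each man first received content. If any content was shown before a city's randomised start, add a supporting analysis that does not treat those city-periods as unexposed control.

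The cost is protocol wording, a messaging setting for each city and one date field, plus the supporting analysis if it is needed. No extra participants or surveys are required.
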